4.8.4 Vital Signs, Physical Findings and Other Observations Related to Safety

1) Definition:

Vital signs (blood pressure, pulse rate, body temperature), body weight and ECG.

ECG parameters will include heart rate, PR interval, QRS complex, QT interval and QTc interval.

2) Analysis Set:

SS

3) Analysis Method ¹³:

The following summaries will be generated:

- A summary of each vital signs, body weight and ECG and its change from baseline by treatment arm and time point.
- A summary of the number and percentage of subjects having QTcF interval values > 450 ms, > 480 ms and > 500 ms at each time point.
- A summary of the number and percentage of subjects having QTcF interval changes from baseline > 30 ms and > 60 ms at each post-baseline time point.
- Shift table of 12-Lead ECG findings at each post-baseline time point and worst in post-baseline assessment

By-subject listings of vital sign parameters and ECG results will also be generated.

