7.2.2.3 Clinical Laboratory Tests (Hematology test, Blood Biochemistry Test) and Urinalysis

The central laboratory will measure the endpoints listed in [Table 7.2.2.3-1](#). The volume of blood sampling is shown in Annex 3.

The investigator or subinvestigator will review the analysis report from the central laboratory, and date and sign the analysis report.

Table 7.2.2.3-1 Clinical Laboratory Tests (Central Laboratory)- Listing	
Hematology Test	Blood Biochemistry Test
Hemoglobin (Hb)	Aspartate transaminase (AST)
Hematocrit (Hct)	Alanine transaminase (ALT)
Red blood cell count (RBC)	Alkaline phosphatase (ALP)
White blood cell count (WBC)	Lactate dehydrogenase (LDH)
Platelet count (PLT)	γ - glutamyltransferase (γ-GTP)
	Total protein (TP)
	Albumin (ALB)
	Total bilirubin (T-BIL)
	Blood urea nitrogen (BUN)
	Uric acid (UA)
	Creatinine (Cr)

Differential leukocyte count (myeloblasts/leukemia cells, lymphoblasts, erythroblasts, monoblasts, promyelocytes, myelocytes, metamyelocytes, neutrophils [Stab cell, segmented cells], basophiles, eosinophils, monocytes, lymphocytes, and atypical lymphocytes) and urinalysis (pH and specific gravity, bilirubin, glucose, ketone bodies, white blood cells, occult blood, protein, urobilinogen) will be measured by each trial site. The date of sampling and the result will be recorded in the medical records and the CRF. For urine collection, the information on whether collection was performed in a fasting state or not will be recorded in the medical records and the CRF.

7.2.2.4 12-Lead Electrocardiography

The investigator or subinvestigator will measure 12-lead ECG parameters according to the procedures of the trial site in the screening period and at least once every four weeks in the treatment period. The central ECG laboratory will electronically collect 12-lead ECG data and determine heart rate, PR interval, QRS complex, QT interval and QTc interval ($QTcF = QT \text{ interval} / [R-R \text{ interval}]^{1/3}$). The central ECG laboratory will report the analysis results to the investigator or subinvestigator. The investigator or subinvestigator will then review the results, and date and sign the analysis report. The investigator or subinvestigator will also reconfirm the normality/abnormality judgment by

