11.3.2 Safety Analysis

1) Definition:

AEs, clinical laboratory tests, vital signs (blood pressure, pulse rate, body temperature), urinalysis, body weight, and electrocardiogram.

2) Analysis Set:

SS

3) Analysis Method

The analysis will be performed by each treatment arm.

Descriptive statistics will be calculated for continuous variables and frequency distributions at each time point will be calculated for categorical variables.

The object of analysis is AE occurrence after the start of IMP administration. AEs will be categorized using the terminology of the Medical Dictionary for Regulatory Activities (MedDRA). AEs will be tabulated by System Organ Class (SOC) and Preferred Term (PT), with PT substituted for verbatim terms. The number of subjects and number of incidence of the following events will be tabulated per arm. A summary of SAEs will be provided by severity.

- Adverse events
- Adverse drug reactions
- Serious adverse events by severity
- Adverse events leading to withdrawal

Severity will be graded using Common Terminology Criteria for Adverse Events (CTCAE) version 4.0.

4) Safety Interim Analysis

For the purpose of data safety monitoring, the safety interim analysis will be conducted regularly on all subjects to provide AE tables, SAE lists, etc, while the level of blinding is being maintained.

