4.8.3 Clinical Laboratory Evaluation

1) Definition:

A subject will be defined as having a treatment-emergent laboratory abnormality if any of the following conditions are satisfied for a specific laboratory parameter.

- A laboratory result within the normal range at baseline and either a result below the lower limit of the normal range or above the upper limit of the normal range at any post-baseline time point.
- A laboratory result below the lower limit of the normal range at baseline and a laboratory result above the upper limit of the normal range at any post-baseline time point.
- A laboratory result above the upper limit of the normal range at baseline and a laboratory result below the lower limit of the normal range at any post-baseline time point.

In addition, laboratory values will be graded using CTCAE version 4.03.

2) Analysis Set:

SS

3) Analysis Method:

The following summaries will be generated:

- A summary of each laboratory parameter and its change from baseline by treatment arm and time point

- Shift table of laboratory parameter (Urinalysis) at each post-baseline point
- A summary of the number and percentage of subjects experiencing low, normal and high values at baseline and at each post-baseline time point (shift table)
- A summary of the number and percentage of subjects with different CTCAE grades at baseline, at each post-baseline time point and worst grade in post-baseline (shift table)
- A summary of new or worsened laboratory abnormalities based on CTCAE Grades (Categories: all grades, Grade 1+Grade 2, Grade 3+Grade 4)
In this table, the worst grade observed in post-baseline are summarised. Patients with no change or better grade from baseline are not counted. 'New' abnormality means 'grade 0' at baseline and '>= grade 1' after baseline. All grade means '>= grade 1' after baseline.

By-subject listings of all laboratory data will be generated by treatment arm with reference range provided and abnormal values will be marked with flags (H/L, Gx).

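### QTcF threshold counts are planned by time point only; one per-subject worst-value table, adjusted for length of follow-up, would give the number in each arm who ever crossed a limit.

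*SAP*

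**What the plan says.** SAP 4.8.4 plans four ECG summaries and a listing:

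- For the continuous parameters: "A summary of each vital signs, body weight and ECG and its change from baseline by treatment arm and time point".
- For absolute QTcF: the number and percentage of "subjects having QTcF interval values > 450 ms, > 480 ms and > 500 ms at each time point".
- For change in QTcF: the number and percentage with "QTcF interval changes from baseline > 30 ms and > 60 ms at each post-baseline time point".
- For findings: "Shift table of 12-Lead ECG findings at each post-baseline time point and worst in post-baseline assessment".
- At subject level: "By-subject listings of vital sign parameters and ECG results will also be generated".

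The two QTcF bullets do not name the treatment arm, but Protocol 11.3.2 sets all safety analysis by arm. It also states that "frequency distributions at each time point will be calculated for categorical variables".

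SAP 4.8.3 tabulates laboratory CTCAE grades "at each post-baseline time point and worst grade in post-baseline (shift table". For adverse events, the by-severity summaries in SAP 4.8.2 use each subject's worst severity. SAP 4.11 (subgroups) and 4.13 (changes from the protocol) add nothing on QTcF.

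**The concern.** Both documents list comparing safety between the arms as a secondary objective. For QTcF outliers, the quantity that supports such a comparison is the number of subjects in each arm who ever crossed a limit. Counts by visit do not give that number. Three subjects above 500 ms once each, at different visits, produce the same rows as one subject above 500 ms at three visits.

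The rows also do not show whether a subject above 450 ms after dosing was already above it at baseline. The SAP uses a per-subject worst value for adverse event severity, laboratory grades and ECG findings, so its absence for the QTcF limits stands out.

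What is at stake is how easily the trial's human QT data can be read. No efficacy endpoint, test or sample size is affected.

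**Working it through.** The documents state no figure on this point, so there is none to reproduce. The check has four steps.

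**1. Number of time points.** The trial schedule (Protocol Table 7.1-1 and Protocol 7.1.3.2.2) places ECGs at Weeks 5, 9 and 13 and then every 4 weeks. The last such visit before the completion examination is Week 101. That gives (101 − 5)/4 + 1 = 25, plus the completion ECG = 26 post-baseline time points for a completer. These are rows within each summary, not 26 separate tables.

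**2. What the rows determine.** Let r_j be the number of subjects above a limit at time point j, and M the number in the arm who ever exceed it at a scheduled visit. Then max(r_j) ≤ M ≤ sum(r_j), with M also capped at the arm size (60 planned per arm, Protocol 3.4).

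- All rows 0: M = 0 exactly.
- A 1 in three rows, 0 elsewhere: M is 1 to 3, or 1/60 = 1.7% to 3/60 = 5.0%.
- A 1 in all 26 rows: M is 1 to 26, or 1.7% to 26/60 = 43.3%.

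**3. Does another planned output supply M?**

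- The shift table of ECG findings has a worst row, but the SAP does not define its categories. Protocol 7.2.2.4 says: "The investigator or subinvestigator will also reconfirm the normality/abnormality judgment by" reference to the central ECG laboratory's report. This suggests normal/abnormal categories rather than millisecond bands.
- Under the same protocol section, clinically significant ECG findings are evaluated as adverse events. Whether one reaches the AE tables depends on that judgment and not on a QTcF limit.
- The by-subject listing holds the values, so M can be derived from it. A listing is not a comparison by arm.

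**4. Does a per-subject maximum compare the arms fairly?** Not by itself. For illustration, assume a chance p per ECG of exceeding a limit, the same in both arms and independent between visits. For a completer, the chance of ever exceeding is 1 − (1 − p)^26. This is 12.2%, 23.0% and 40.9% for p = 0.5%, 1% and 2%.

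Now let follow-up end at a DFS event, exponential with the 2-year rates in Protocol 11.5: 20% on placebo, and 35% to 40% on OCV-501 (20% plus 15 to 20 points). Give each subject one final ECG. The hazard is λ = −ln(S2)/2 per year, and mean ECGs = 1 + Σ exp(−λt) over the 25 visits. That is about 13 (S2 = 20%), 16 (35%) and 17 (40%). The share ever exceeding is 1 − E[(1 − p)^N], where N is the number of ECGs:

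| p per ECG | Placebo, S2 = 20% | OCV-501, S2 = 35% | OCV-501, S2 = 40% |
|---|---|---|---|
| 0.5% | 6.4% | 7.8% | 8.2% |
| 1% | 12.2% | 14.9% | 15.6% |
| 2% | 22.4% | 27.0% | 28.3% |

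The per-ECG risk is equal by construction, so the whole difference between columns comes from unequal follow-up. A rate of first exceedance removes most of it. With ECGs 28 days apart, p = 1% corresponds to about 0.01 × 365.25/28 = 0.13 first exceedances per person-year in both arms. If the same subjects exceed every time, the share ever exceeding is simply p in each column, and both the arm difference and the gap from the per-visit rows disappear.

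**The case against.** The strongest case is that this is a choice of format. Protocol 11.3.2 asks for frequencies by time point, and the SAP follows it. In SAP 4.8.3 the low/normal/high and urinalysis shift tables also have no worst row, so QTcF is not the only item treated this way. This stands: the SAP does not breach the protocol, and the contrast is with some of its safety tables, not all.

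Four stronger readings are tempting, and the documents do not support them.

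- *The per-subject figure cannot be obtained.* It is bounded by the rows, is exactly zero if all rows are zero, and can be derived from a listing of about 120 subjects.
- *Subjects already above 450 ms are hidden.* The absolute-value bullet covers every time point, while the change bullet is limited to post-baseline ones. Baseline is therefore plausibly a row of the first table. Only the within-subject link is missing.
- *The worst-finding shift table certainly omits the QTcF limits.* That is a likely inference. The SAP refers to output shells, which are not part of the documents.
- *The illustrative percentages point to a QT risk.* They rest on assumed rates. The protocol describes low systemic exposure and no ECG effect in dogs (1.2.1.2), and gives little reason to expect a signal.

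The objection that a per-subject maximum favours the arm with shorter follow-up is correct and changes the remedy. Printing the ECG count beside the table discloses the problem but does not correct it.

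**Conclusion.** The concern holds as a minor safety-reporting improvement. On the SAP text, no planned table gives the number of subjects per arm who ever exceeded 450, 480 or 500 ms or rose by more than 30 or 60 ms, and none cross-classifies the post-baseline category by the baseline category. With 26 time points the per-visit rows bound that number. The bounds are tight if exceedances are few and wide if they are scattered over many visits.

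The counting argument rests only on the schedule. The percentages rest on assumed per-ECG rates and on independence between visits, and they count only DFS events as ending follow-up, so other withdrawals would lower the ECG counts. They show how a maximum behaves under unequal follow-up and say nothing about a drug effect. The conclusion could change if the output shells already contain a worst-value row.

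**What to change.** Keep the per-visit counts and add to SAP 4.8.4, by arm:

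1. Each subject's maximum post-baseline QTcF (≤450, >450–480, >480–500, >500 ms), cross-classified by baseline category.
2. Each subject's maximum increase from baseline (≤30, >30–60, >60 ms).
3. The number of post-baseline ECGs per subject, with either first exceedances per person-year for each limit or the same table restricted to a common early window fixed before unblinding. A window reduces the follow-up imbalance but does not fully remove it, because subjects also leave within the window.

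State whether unscheduled ECGs count towards the maximum. SAP 4.2 keeps extra assessments out of summaries, but the data types it names there do not include ECGs.

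The cost is one table and a short rate calculation from ECG data already collected centrally. The remaining downside is that the maximum can be misread if quoted without the follow-up-adjusted figure, so the two should appear together.

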4.9 Safety Interim Analysis

For the purpose of data safety monitoring, the safety interim analysis will be conducted regularly on all subjects while the level of blinding is being maintained.

The following summaries will be generated.

- A summary of patient background
- A summary of treatment compliance (overall and until withdrawal)
- A summary of number and percentage of subjects reporting a TEAE by SOC and PT
- A summary of number and percentage of subjects reporting a TEAE by CTCAE severity grade, SOC and PT

The following by-subject listings will be generated.

- A by-subject listing of all SAEs other than death
- A by-subject listing of all deaths

Also, the following graphs will be generated.

- Kaplan-Meier curve of DFS
- Kaplan-Meier curve of OS

4.10 Exploratory Items Analysis

1) Definition:

OCV-501 specific IFN- γ production, WT1-killer peptide specific IFN- γ production, anti-OCV-501 antibody level, anti-WT1 antibody level, WT1 mRNA level and immunoglobulin

2) Analysis Set:

IRS

3) Analysis Method:

Generally, a summary will be calculated in terms of the mean, geometric mean, SD, coefficient of variation, median, minimum, maximum and number of patients, unless otherwise stated.

At each time point, a summary of each exploratory parameter and change from baseline will be generated and time courses of immune response values will be plotted by treatment arms.

4.11 Subgroup Analysis

1) Definition:

DFS, OS, safety (Summary of TEAE, TEAE by MedDRA SOC and PT) and exploratory parameters will be examined for the following subgroups.

Table 4.11-1 Subgroup	
Factor	Categories
Country/ Region	Japan, Republic of Korea, and Taiwan
Age	60 to 64 years, 65 to 70 years, ≥ 71 years

2) Analysis Set:

FAS for DFS and OS, SS for safety, IRS for Immune response

3) Analysis Method:

For each subgroup, the following statistical analyses will be performed.

DFS/OS: log-rank test, HF test, KM estimates of DFS/OS rate

Safety: Summary of TEAE, Incidences of TEAE by MedDRA SOC and PT

Exploratory parameters: Summary of descriptive statistics

4.12 Determination of Sample Size

The number of AML patients is not very high, and is estimated to be approximately 7000 in Japan⁷. From the fact that in the previous clinical trial (JALSG GML200) in elderly AML patients, it has been forecast that the possible enrollment in Japan is to be at most 70 in one year. Also, from the preliminary trial feasibility survey, it is known that around 50 subjects could be recruited in one year in the Republic of Korea and Taiwan. Through a global trial in Japan, the Republic of Korea and Taiwan, it is considered possible to enroll 120 subjects in one year to assess the efficacy of OCV-501.

Within the limitation of the past experiences with regard to IMP administration, the target sample size will be considered with reference to following publications.^{5,6,7,9} With reference to disease-free survival which has been reported from trials in AML patients 60 years or older who have received the consolidation therapy followed by maintenance therapy, the 2-year DFS rate of placebo arm has been estimated to be around 20%.^{5,6,7}

On the other hand, considering the so-called graft-versus-leukemia (GVL) effect associated with a lower relapse risk after the allogeneic hematopoietic stem cell transplantation, OCV-501 is basically expected to have the same benefits. With reference to the findings of Kurosawa et al,⁹ which have reported a 30% higher 2 or 3-year DFS in elderly AML subjects who have received the allogeneic hematopoietic stem cell transplantation compared with those without transplantation, OCV-501 is expected to have a 15% - 20% higher 2-year DFS. Under the assumption of exponential distribution of DFS time, the hazard ratio (placebo vs. OCV-501) has been set to 0.57 - 0.65, and with a two-sided log-rank test at the 5% significance level, 60 or more subjects in each treatment group can achieve a power of 53% - 75% or more to detect the difference between placebo and OCV-501 groups.

4.13 Changes in the Conduct of the Study or Planned Analysis

Any changes made after the database lock will be recorded in the relevant section of the clinical study report.

Changes from the analysis planned in the protocol are as follows:

Section number	Contents of changes	Reason of changes
4.5 Demographics and Other Basic Characteristics	WT1 mRNA level at Day 1 was added instead of AML diagnosis or at the time of induction therapy or consolidation therapy.	Day 1 data would be more influential than the data at diagnosis or at the time of induction or consolidation therapy.
4.7.1.1 DFS 4.7.2.1 OS	Proportionality assumption will be tested first. Cox PH model will be conducted on every 3 month interval as an alternative analysis.	If proportionality assumption fails, then Cox PH model might be considered invalid to conduct on the whole period.

Section number	Contents of changes	Reason of changes
4.7.1.1 DFS 4.7.2.1 OS	Age, country and other factor (WT1 mRNA) will be adjusted as covariates in the Cox PH model. Furthermore, subgroup analysis will be conducted.	Cox PH model analyses adjusted by covariates are added to investigate the influence of covariates. And the subgroup analyses are added as supplementary analyses.
4.7.2.2 QOL	Mixed-effect model repeated measures will be conducted.	To make a comparison on QOL between two treatment arms.
4.7.2.3 PS	Improvement factor will be created and Wilcoxon 2-sample test will be conducted.	To make a comparison on PS between two treatment arms.
4.7.3. Reference efficacy endpoint 4.7.3.1 DFS until OS cutoff date 4.7.3.2 Therapeutic Response	New efficacy variables have been added.	For the purpose of reference
4.8.2 Adverse Events	A summary of SAEs by severity is not conducted.	Listing will cover it.
4.10 Exploratory Items Analysis	For WT1 mRNA item, t-test is not conducted.	According to the nature of WT1mRNA data, comparison between treatment arms will not be necessary.
4.11 Subgroup analysis	Safety and immune response have been added to the subgroup analysis.	For the purpose of reference

